## **5. Risks and Safety as adverse events**

### **5.1 Known potential risks**

This study is conducted with CE-marked devices, so all risks identified are mitigated as low as possible and are below the risk acceptability threshold. Residual risks are presented in the user instructions (if applicable) and there is no new risk due to study-related measures.

The risk management process for the hearing aid system is performed in accordance with the requirements stated in ISO 14971. The identified risks and mitigations for the hearing aid system conducted by the Sponsor is documented in the Signia Pure C&G T IX User Guide (see Appendix 16.1) and in the Safety manual for hearing aids Master (see Appendix 16.1).

There are no new risks due to study-related measures.

In conclusion, the overall residual risk is acceptable for this PMCF study using the PURE C&G T 7IX M hearing aid and Connexx 9.11 fitting software.

### **5.2 Known potential benefits**

Hearing aids relieve the strain of hearing, i.e., less strain and more clear hearing. It is anticipated that inexperienced wearers will experience improved ease and better speech understanding in various listening environments, e.g., watching television, conversations.

Subjects get the chance to try out state-of-the-art modern hearing aids. Subjects already fitted with hearing aids will gain experience with hearing aids.

During screening the hearing of the subjects is checked by a hearing care professional thus the subjects gain current information about the status of their hearing.

Having to participate in laboratory speech tests and filling in surveys during the study may have the benefit that subjects pay more attention to their hearing which might lead to increased perceptiveness of sound being an incentive to become more socially active. Overall, this could contribute to their emotional well-being.

### **5.3 Adverse Events and Serious Adverse Events**

Unaffected by handling AEs and SAEs within the scope of the study, the provisions and reporting deadlines of the corresponding legal regulations (MDR, MPDG, MPMIV) apply to incidents (=Vorkommnisse") involving medical devices.

### 5.3.1 Definition of adverse events (AE)

Adverse event, as defined according to ISO1455, means any untoward medical occurrence, unintended disease or injury, or untoward clinical signs (including abnormal laboratory findings) in subjects, users or other persons, whether or not related to the investigational medical device and whether anticipated or unanticipated.

Note 1: This definition includes events related to the investigational device or comparator.

Note 2: This definition includes events related to the procedures involved.

Note 3: For users or other persons, this definition is restricted to events related to the use of investigational medical devices or comparators.

An Adverse event related to the use of an investigational medical device is called an Adverse Device Effect. This definition includes adverse events resulting from insufficient or inadequate instructions for use, deployment, implantation, installation, or operation, or any malfunction of the investigational medical device. This definition includes any event resulting from use error or from intentional misuse of the investigational medical device. It also includes comparator if comparator is a medical device.

### 5.3.2 Definition of serious adverse events (SAE)

A Serious Adverse event is an adverse event that led to any of the following:

a) death,  
b) serious deterioration in the health of the subject, users, or other persons as defined by one or more of the following:

- 1) a life-threatening illness or injury, or
- 2) a permanent impairment of a body structure or body function including chronic disease, or
- 3) in-patient or prolonged hospitalization, or
- 4) medical or surgical intervention to prevent life-threatening illness or injury or permanent impairment to a body structure or a body function,

c) fetal distress, fetal death or a congenital abnormality or birth defect including physical or mental impairment

*Note: Planned hospitalization for a pre-existing condition, or a procedure required by the study, without serious deterioration in health, is not considered a SAE.*

Unanticipated serious adverse device effect (USADE) is a serious adverse device effect which by its nature, incidence, severity, or outcome has not been identified in the current risk assessment.

Note: Anticipated serious adverse device effect (ASADE) is an effect which by its nature, incidence, severity or outcome has been identified in the risk assessment.

### 5.3.3 Classification of an adverse event

#### 5.3.3.1 Severity of event

For adverse events (AEs) the following guidelines will be used to describe severity.

- **Mild** – Events require minimal or no treatment and do not interfere with the subject's daily activities.
- **Moderate** – Events result in a low level of inconvenience or concern with the therapeutic measures. Moderate events may cause some interference with functioning.

- **Severe** – Events interrupt a subject’s usual daily activity and may require systemic drug therapy or other treatment. Severe events are usually potentially life-threatening or incapacitating. Of note, the term “severe” does not necessarily equate to “serious”.

#### **5.3.3.2 Relationship to study intervention**

All adverse events (AEs) must have their relationship to study intervention assessed by the clinician who examines and evaluates the subject based on temporal relationship and his/her clinical judgment. The degree of certainty about causality will be graded using the categories below. In a clinical trial, the study product must always be suspect.

- **Related** – The AE is known to occur with the study intervention, there is a reasonable possibility that the study intervention caused the AE, or there is a temporal relationship between the study intervention and event. Reasonable possibility means that there is evidence to suggest a causal relationship between the study intervention and the AE.
- **Not Related** – There is not a reasonable possibility that the administration of the study intervention caused the event, there is no temporal relationship between the study intervention and event onset, or an alternate etiology has been established.

#### **5.3.3.3 Expectedness**

The Sponsor will be responsible for determining whether an adverse event (AE) is expected or unexpected. An AE will be considered unexpected if the nature, severity, or frequency of the event is not consistent with the risk information previously described for the study intervention.

#### **5.3.4 Time period and frequency for event assessment and follow-up**

The occurrence of an adverse event (AE) or serious adverse event (SAE) may come to the attention of study personnel during study visits and interviews of a study subject presenting for medical care.

All AEs, including local and systemic reactions not meeting the criteria for SAEs, will be captured on the appropriate case report form (CRF). Information to be collected includes event description, time of onset, clinician’s assessment of severity, relationship to study product (assessed only by those with the training and authority to make a diagnosis), and time of resolution/stabilization of the event. All AEs occurring while on study must be documented appropriately regardless of relationship. All AEs will be followed to adequate resolution.

Any medical condition that is present at the time that the subject is screened will be considered as baseline and not reported as an AE. However, if the study subject’s condition deteriorates at any time during the study, it will be recorded as an AE.

#### **5.3.5 Adverse event reporting**

The investigator must record non-serious adverse events and report them to the Sponsor in a timely manner after the investigator first learns of the adverse event. AEs which are non-serious and not related to the research procedures do not have to be reported to the ethics committee but will be reviewed by the Sponsor.

In case however that the event is unexpected AND more likely than not related to the research procedures it shall be reported to the ethics committee within 5 days of Investigator receiving notice of the event.

### **5.3.6 Serious adverse event reporting**

The study investigator shall report an Unanticipated Adverse Device Effect to the study sponsor and to the reviewing ethics committee as soon as possible, but in no event later than 5 working days after the investigator first learns of the effect. The study sponsor is responsible for conducting an evaluation of an unanticipated adverse device effect and shall report the results of such evaluation to the ethic committee within 10 working days after the sponsor first receives notice of the effect.

The sponsor must immediately conduct an evaluation of any unanticipated adverse device effect.

If the sponsor determines that an unanticipated adverse device effect presents an unreasonable risk to subjects, the sponsor must terminate all investigations or parts of the investigations presenting that risk as soon as possible. Termination must occur no later than 5 working days after the sponsor makes this determination and no later than 15 working days after the sponsor first received notice of the effect.

#### **Resumption of Terminated Studies:**

For a nonsignificant risk device investigation, a sponsor may not resume a terminated investigation without ethics committee approval. If the nonsignificant risk study was terminated for unanticipated adverse device effects, the sponsor must also obtain ethics committee approval.

[figure not shown]
## **6. Design of the clinical investigation**

### **6.1 Subjects**

The test will be conducted with 20 mild to moderately hearing-impaired listeners (HIL) in the fitting range of an M-receiver.

#### **Inclusion criteria:**

- The allowed audiometric range for HIL is shown below:

- They should be experienced hearing aid users
- Air-Bone-Gap should be less or equal to 20 dB HL.
- Sensorineural HV, mild-to-moderate
- HV corresponding to the fitting range of the HA
- Healthy (outer) ear
- Older than 18 years
- German is mother tongue
- Able to understand the instructions
- Willing to participate in laboratory tests and to wear the HAs at home for 2 weeks
- Informed consent

**Exclusion criteria:**

- Contraindication for HA treatment
- Fluctuating or rapidly progressing hearing loss
- “Central” hearing problems
- Limited mobility
- Limited dexterity (in handling the HA)
- Known psychological problems
- They must not show any injuries or a complete perforation of the ear drum. This must be clarified prior to the beginning of the study by means of otoscopy.
- They should be quite healthy (e.g., they shall not suffer from dementia) and should not use medical treatments that might affect study results.

Any deviations from the above requirements must be noted and justified.

Additionally, both women and men should take part in the study. Also, the hearing loss of the subjects should be roughly distributed over the fitting range of the hearing aids (not covering the extremes is permitted).

## 6.2 Devices & Fitting

The test will be conducted with CE-marked **PURE C&G 7IX M** devices.

Study HA are first fitted according to individual hearing loss, using released fitting software Connexx 9.11. Fitting formular for REM Measurements is NAL NL2. Fine Tuning to target will be done via AutoFit Feature in Connexx. After REM Measurements First Fit will be repeated with proprietary formula IXFit. Fine-tuning should be done as required by standard-of care (best practice) before sending the subjects to the home trial. Adding extra programs is allowed if requested by the subject (best practice). In the second lab session after the home trial and before the speech tests are performed, subjects will be asked if further fine-tuning is needed.

If the subject wishes for the use of Signia App as remote control during the Home Trial, the subjects are shown how to download the Signia App and the study HAs are coupled with the subject's own smartphone to support e.g. volume control via Signia App during the home trial.

## 6.3 Workflow

All subjects will participate in two lab sessions as described below. Sessions should not exceed 90 min per subject. Additionally, subjects will do a home trial to rate subjective perception in relevant daily-life situations.

1 st lab trial Fit-to-Target	1 st Home Trial Study HAs	2 nd Lab Trial Speech tests	2 nd Home Trial Own HAs

• Audiometry & Anamnesis

• Fit to NAL_NL2

• Real-Ear Measurements

• ISTS @55/65/80 dB SPL

• Document Match-to Target

• New fitting to proprietary Rationale

• Listen to HAs in quiet and conversation and fine-tune as needed

	

• Duration 10-14 days

• Use HAs in daily life environments

• Option to come back for fine-tuning if needed

• At the end of home-trial fill out questionnaires:

◦ SSQ 17

◦ IOI-HA

◦ Satisfaction

◦ Basic User Needs

	

• Perform fine-tuning upon request

• Speech test in quiet (Freiburger @65 dB SPL)

◦ Unaided

◦ Study HAs

◦ Own HAs

• Speech test in noise (OLSA, SRT 80%, OL noise @65 dB SPL)

◦ Unaided

◦ Study HAs

◦ Own HAs

	

• Duration 10-14 days

• Use HAs in daily environments

• At the end of home-trial fill out questionnaires:

◦ SSQ-17

◦ IOI-HA

◦ Satisfaction

• Return questionnaires via mail

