## **7.2 Statistical analysis**

**Objectives 1 and 2** (Speech in Noise OLSA): The SRT data will be analyzed using a one-tailed paired t-test.

**Objectives 3 and 4** (Speech in Quiet Freiburger): Similarly to the OLSA Test the % correct data will be analyzed using a one-tailed paired t-test.

**Objective 5** (NAL-NL2 Targets): No statistical analysis will be performed, only descriptive statistics will be used.

**Objectives 6-7** (Questionnaires – SSQ17, IOI-HA)

Subjective rating data from real-life questionnaires will be analyzed using one-tailed paired t-tests, comparing ratings of study HA and own HA with a significance level of 0.05 to determine significance.

In addition, descriptive statistics of the SSQ 17 scores and IOI-HA scores will be reported by Hearing Aid (study or own) for each subscale and put into perspective of published data (von Gahlenz et al, 2018; Cox et al, 2013).

**Objective 8** (Questionnaire – Satisfaction)

One-sided test of proportions will be done to analyze whether the proportion of satisfied hearing aid users is significantly lower with study hearing aids than reported in the literature (MarkeTrak 10, EuroTrak). A significant effect indicates that the study hearing aids are inferior, otherwise they are non-inferior.

In addition, subjective rating data from satisfaction questionnaire will be analyzed using one-tailed paired t-tests, comparing ratings of study HA and own HA with a significance level of 0.05.

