### **9.4 Randomization and blinding coding**

The study design does not allow for the study to be blinded. REM Measurements will only be done with the study HAs and during Home-Trial, subjects are well aware of which HA they are wearing. For the speech tests the order of study HA, own HA and unaided will be randomized.

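### Every subject rates the study aids first and their own aids second, so the study-versus-own questionnaire tests cannot separate device from period

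*Combined protocol and SAP*

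**What the plan says.** The workflow table in section 6.3 describes a single sequence: fitting at lab session 1, then "Home Trial Study HAs", then lab session 2 with the speech tests, then "Home Trial Own HAs". Each home trial lasts 10–14 days and ends with SSQ17, IOI-HA and the Satisfaction questionnaire. No second sequence group, washout or pre-fitting rating of the own aids is described.

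Section 9.4 limits randomisation to the laboratory: "For the speech tests the order of study HA, own HA and unaided will be randomized".

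Section 7.2 sets the analysis for Objectives 6 and 7: "Subjective rating data from real-life questionnaires will be analyzed using one-tailed paired t-tests, comparing ratings of study HA and own HA", at a 0.05 significance level. For Objective 8, "subjective rating data from satisfaction questionnaire will be analyzed using one-tailed paired t-tests", alongside a separate test against published satisfaction rates. Under section 4.2.2, a significantly worse rating means the study aids are inferior; any other result is read as non-inferior.

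**The concern.** Device and period coincide in every subject. Own-aid ratings are always given in the second period, after wearing the study aids, after speech testing with both devices in session 2, and on a second completion of the same forms. If any of these moves ratings, the movement enters the device comparison in full, in either direction, and does not shrink with more subjects.

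At stake are the inferior or non-inferior statements about ratings against own aids. These are secondary: section 1.4 states the main objective as speech understanding, and section 7.1 sizes the trial on Objective 1. The overall hypothesis in section 1.4 does, however, include performance ratings against own aids.

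Not affected are Objectives 1–5, Objective 8's test against published rates, and the descriptive setting of study-aid SSQ17 and IOI-HA scores "for each subscale and put into perspective of published data". Novelty, lack of blinding and prior use of the own aids ("They should be experienced hearing aid users") are present in either order and are not part of this point.

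**Working it through.** **The plan's own figures.** Section 7.1 gives none for the questionnaires. Its figures for Objective 1 reproduce for dz = 0.77 with a two-sided 0.05 test: power is 0.821 at n = 16 and 0.904 at n = 20. Only the two sample sizes are carried forward: 20 recruited, and 16 before the dropout allowance.

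**Can device be separated from period?** Take a linear model with 20 subject terms, one device term and one period term, 22 parameters in all. Under the fixed order the design matrix has rank 21, so device and period are not separately estimable. With a 10/10 split between two orders, the rank is 22.

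**What the paired difference estimates.** Let d be the device effect, p the period-2 effect, l the effect of lab session 2, cS the carry-over of study-aid wear into own-aid ratings, and cO the effect of prior own-aid use on study-aid ratings.

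- Planned design, study minus own: d − p − l − cS + cO.
- Counterbalanced, study-first subjects: d − p − l − cS + cO.
- Counterbalanced, own-first subjects: d + p + cO.
- Average of the two sequence means: d − l/2 − cS/2 + cO.

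**When the planned test declares inferiority.** The observed mean deficit, in SDs of the paired difference, must exceed t(0.95, n−1)/√n:

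- n = 20: 1.729/4.472 = 0.387 SD.
- n = 16: 1.753/4 = 0.438 SD.

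An order shift moves the mean one for one against these thresholds.

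**Illustration.** The documents give no rating SD and no order effect, so the shifts below are assumed. Entries are noncentral-t probabilities of declaring inferiority, one-sided 0.05, for the planned fixed order.

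| Assumed shift (SD) | 0 | 0.1 | 0.2 | 0.3 | 0.4 |
|---|---|---|---|---|---|
| True deficit 0.5 SD, shift favours study aid, n = 20 | 0.695 | 0.532 | 0.363 | 0.217 | 0.112 |
| True difference 0, shift against study aid, n = 20 | 0.05 | 0.112 | 0.217 | 0.363 | 0.532 |
| True deficit 0.5 SD, shift favours study aid, n = 16 | 0.604 | 0.453 | 0.309 | 0.189 | 0.103 |
| True difference 0, shift against study aid, n = 16 | 0.05 | 0.103 | 0.189 | 0.309 | 0.453 |

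**What counterbalancing recovers.** For an assumed 0.3 SD shift with 10 subjects per sequence (18 df):

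| Source of the shift | Shift remaining (SD) | Detection of a 0.5 SD deficit | False inferior rate |
|---|---|---|---|
| All p | 0 | 0.694 | 0.05 |
| All l or all cS | 0.15 | 0.445 | 0.159 |
| All cO | 0.3 | 0.217 | 0.362 |

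**Its cost in precision.** The standard error of the unweighted average is 0.5·√(1/n₁ + 1/n₂), in SDs of the paired difference.

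| Split | Standard error | df | Power at 0.5 SD | Planned fixed order, same total n |
|---|---|---|---|---|
| 10/10 | 0.224 | 18 | 0.694 | 0.695 |
| 8/8 | 0.250 | 14 | 0.60 | 0.604 |
| 10/6 | 0.258 | 14 | 0.578 | 0.604 |

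**The case against.** The best case against acting is that the harm is unquantified. The documents offer no reason to prefer a shift of 0.4 SD to none, and the comparison is secondary. This stands as a limit on the weight of the point. It does not answer it, because the planned data could not show whether the order effect is zero.

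A second objection is that counterbalancing is only partial. That is correct: it halves session-2 and study-aid carry-over effects, and the algebra assumes that prior own-aid use acts equally in both sequences, which nothing in the documents establishes. Own-first subjects would have formally rated their own aids just before the study aids.

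Third, the verdicts would stay fragile. With no order effect at all, a true 0.5 SD deficit is labelled non-inferior with probability 1 − 0.695 = 0.305 at n = 20 and 1 − 0.604 = 0.396 at n = 16, because section 4.2.2 sets no margin. That is a separate defect, which this fix leaves in place.

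Fourth, section 12 restricts publication to descriptive statistics, which may limit how far the verdicts travel. The order effect sits in the means as well, so descriptive reporting does not remove it.

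**Conclusion.** The point holds. In the study-versus-own rating tests for Objectives 6 and 7 and the paired part of Objective 8, device and period are completely confounded. This follows from the workflow and needs no assumption about size. The size and direction in this trial are unknown; the probabilities above rest on assumed shifts of 0 to 0.4 SD, an assumed 0.5 SD deficit and normal paired differences, and the conclusion does not depend on them. This is an inexpensive improvement to a secondary comparison that should be made, not a threat to the primary result.

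**What to change.** **Main change.** Randomise home-trial order 1:1, 10 study-first and 10 own-first. Hold lab session 2 straight after the study-aid period in both sequences, so that the primary speech tests keep their planned timing relative to study-aid wear. Estimate study minus own as the unweighted average of the two sequence means. Own-first subjects will still hear the study aids at the session 1 fitting, and novelty, prior own-aid use and lack of blinding remain.

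**Cost.** An ethics-committee amendment (section 10) and a second randomisation list. For own-first subjects, session 2 falls 10–14 days later, the device loan may be that much longer, and an extra handover or fine-tuning contact may be needed. No extra subjects are required.

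**Lighter alternative.** Keep the order, but also collect the three questionnaires for the own aids before the study aids are fitted. Report study minus baseline-own and own-minus-own with confidence intervals as a sensitivity analysis, and state the fixed order as a limitation of the rating conclusions. This needs the same amendment step and one more questionnaire set, completed at home beforehand if session 1 would otherwise overrun. It is weaker: baseline forms do not follow a matched home trial, so own-minus-own mixes setting with period. Its 95% half-width is 2.093/√20 = 0.468 SD of that difference at n = 20, or 2.131/4 = 0.533 SD at n = 16.

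**Reconcile in the same amendment.** Section 1.4 describes one home trial and section 6.3 two. Section 1.4 allows visits of up to two hours, while section 6.3 says "Sessions should not exceed 90 min per subject".
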